10.3. Deaths, Serious Adverse Events and other Significant Adverse Events

The number and percentage of subjects experiencing adverse events of special interest will be tabulated by study arm as presented in Table 131. The following listings will be presented including Subject ID, AE Description, AE Onset Date/End Date, Last Vaccination Received/Days Post Vaccination, Reason Reported as an SAE, Relationship to Treatment, Alternate Etiology if not Related, Outcome, and Duration of Event (days):

- Deaths and Serious Adverse Events (Table 149)
- Non-Serious, Unsolicited, Moderate or Severe Adverse Events (Table 150)
- Adverse Events of Special Interest (Table 151)

10.4. Vital Signs and Physical Evaluations

Vital signs will be tabulated by study arm in Table 152. A listing of vital signs will be presented (Listing 13). Targeted physical examinations will be performed, if indicated, based on a subject's medical history. A listing of physical exam findings will be presented (Listing 14).

11. TERTIARY AND EXPLORATORY PROTEOMICS ANALYSES

Analysis of tertiary and exploratory endpoints will be described in separate addenda to this SAP which will be finalized prior to analysis of the proteomics data.

12. EXPLORATORY CORRELATION ANALYSES

Correlation analysis between the -omics data (transcriptomics and proteomics) and serum antibody/plasma cytokines as well as correlated with certain safety profiles will be described in separate addenda to this SAP which will be finalized prior to the proteomics data lock.

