5. To identify transcriptomic and proteomic signatures in human immune cells that correlate with influenza seroconversion and with peak HAI titers.
6. To correlate plasma cytokine profiles with transcriptomic and proteomic profiles in subjects receiving influenza A/H3N2v vaccine or influenza A/H7N9 \pm AS03 vaccine.
7. Exploratory inspection of transcriptomics\proteomics response signatures for subjects with unexpected or severe safety profiles that are related to the study products.

Exploratory Outcome Measures

1. RNA expression, clusters of co-expressed genes, enriched pathways, and other functional modules as determined by RNA-Seq analysis, in human immune cells at Days 2, 4, 29, 30, 32, and 36 after study vaccination with AS03-adjuvanted and unadjuvanted A/H7N9 vaccine comparing changes in RNA expression between treatment arms (A/H7N9 vaccine vs. A/H7N9 vaccine + AS03).

2. Protein abundance, clusters of co-abundant proteins, enriched pathways, and other functional modules as determined by quantitative proteomics analysis, in human immune cells at Days 2, 4, 29, 30, 32, and 36 after study vaccination with AS03-adjuvanted and unadjuvanted A/H7N9 vaccine comparing changes in protein abundance between treatment arms (A/H7N9 vaccine vs. A/H7N9 vaccine + AS03).
3. RNA expression, clusters of co-expressed genes, enriched pathways, and other functional modules as determined by RNA-Seq analysis, in human immune cells at Days 2, 4, and 29 after study vaccination comparing baseline changes in RNA expression between treatment arms (A/H3N2v vaccine vs. A/H7N9 vaccine and A/H3N2v vaccine vs. A/H7N9 vaccine + AS03).
4. Protein abundance, clusters of co-abundant proteins, enriched pathways, and other functional modules as determined by quantitative proteomics analysis, in human immune cells at Days 2, 4, and 29 after first study vaccination comparing baseline changes (Days -7, and 1) in protein abundance between treatment arms (A/H3N2v vaccine vs. A/H7N9 vaccine and A/H3N2v vaccine vs. A/H7N9 vaccine + AS03).
5. Changes from baseline (Days -7, 1, and 29) in RNA expression or protein abundance that best correlate with influenza A/H7N9 seroconversion and with peak HAI titers at Days 2 and 4 (following first study vaccination) as well as Days 30, 32, and 36 (following second study vaccination).

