11.5 Final Analysis Plan

Prior to database lock, a Statistical Analysis Plan that will outline in detail the planned statistical analyses for this study will be developed and finalized. In the following section an abbreviated version is provided.

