11.5.4 Primary Clinical Study Report (CSR) Database Lock

Clinical, safety, and reactogenicity data through approximately 28 days after the last study vaccination will represent the primary clinical database for this study. Once the last subject completes the visit that occurs approximately 28 days after the last study vaccination, the primary clinical database will be cleaned, monitored and locked. Unblinded analyses of safety, reactogenicity, and available immunogenicity data may be performed by the SDCC after the primary clinical database is locked. These analyses will be made available to the sponsor for planning subsequent studies and to the clinical investigators for publication. These analyses will not be used to make any decisions concerning the conduct of this study. As it is anticipated subjects will remain in the long-term, tertiary safety follow-up at the time of these analyses, the presentation of these data will be in a format that prevents inadvertent unblinding of the sponsor or clinical investigators to any individual subject's treatment assignment or immune response data. When it is not possible to display the data by treatment arm and maintain the blind for the

clinical investigators and sponsor, such as the presence of extreme values or noteworthy AEs, a presentation by treatment arm will not be provided until after the long-term, tertiary safety follow-up is complete.

Serologic immunogenicity data from HAI and Neut antibody assays and processed cellular immunogenicity data from systems biology studies may be analyzed as results are available once the primary clinical database is locked. These analyses will be considered the final results for this study and included as part of the clinical study report (CSR).

The primary CSR will be completed when all primary and secondary endpoint data are available. Any available data from the long-term, tertiary safety follow-up of applicable subjects may also be included. Additional data from the long-term, tertiary safety follow-up of applicable subjects, exploratory correlation analyses, and data from the proteomics portion of the study will be included in one or more addenda to the CSR.

A formal statistical analysis plan will be developed and finalized prior to database lock.

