6.2. Timing of Analyses

The primary CSR will be completed when all primary and secondary endpoint data are available and the data have been cleaned and locked. Any available data from the long-term, tertiary safety follow-up of applicable subjects may also be included. Additional data from the long-term, tertiary safety follow-up of applicable subjects, exploratory correlation analyses, and data from the proteomics portion of the study will be included in one or more addenda to the CSR.

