10. SAFETY EVALUATIONS

Summaries and analysis of safety data will be presented for the Safety Analysis Population. These include reactogenicity following each study vaccination, unsolicited adverse events, and adverse events of special interest including SAEs/MAAEs, new-onset chronic medical conditions, and potentially immune-mediated medical conditions. The goal of the safety summaries is to provide information to guide the exploratory correlation analysis to identify transcriptomic/proteomic changes that are predictive of certain safety profiles. The exploratory correlation analysis will be described in an addendum to this SAP. The following sections describe planned baseline and safety summaries.

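### The deadline for the RNA-Seq correlation plan is tied to the proteomics lock, which does not protect it, and the safety outcome is left to be chosen from safety summaries that may already be unblinded

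*SAP*

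**What the plan says.** SAP 12 defers the whole correlation analysis, transcriptomic and proteomic, against antibody, cytokine and safety data. It "will be described in separate addenda to this SAP which will be finalized prior to the proteomics data lock". SAP 11 sets a similar trigger for the tertiary and exploratory proteomics addenda, which are to be "finalized prior to analysis of the proteomics data".

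SAP 10 gives the safety summaries a role in that later work. They are to "provide information to guide the exploratory correlation analysis to identify transcriptomic/proteomic changes that are predictive of certain safety profiles". The profiles themselves are not defined in SAP 10, in SAP 12 or in SAP 3.2 (exploratory endpoint 7).

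Protocol 11.5 sets the general rule: "Prior to database lock, a Statistical Analysis Plan that will outline in detail the planned statistical analyses for this study will be developed and finalized". On access to results, Protocol 11.5.4 says: "Unblinded analyses of safety, reactogenicity, and available immunogenicity data may be performed by the SDCC after the primary clinical database is locked". SAP 6.2 puts the primary CSR at the point when all primary and secondary data are available and locked, and reports the rest later: "exploratory correlation analyses, and data from the proteomics portion of the study will be included in one or more addenda to the CSR".

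**The concern.** A deadline for a plan protects against selection only if it falls before the relevant results are known. Correlating RNA-Seq responses with antibody, cytokine or safety data uses no proteomics data, so locking the proteomics data later does nothing for that part. Where an outcome is still undefined, it can be picked because it separates the arms or looks promising in the CSR tables. SAP 10 goes further for safety, because it makes guidance from the safety tables part of the plan.

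At stake is how far a reported signature can be believed. The Benjamini-Hochberg control in SAP 6.8 covers genes, proteins and pathways within a model. It does not cover the choice of the outcome being modelled. A gene signature described as predictive of a reactogenicity profile that was chosen from the same 30 subjects would have a higher false-positive rate than its adjusted p-values suggest, and readers could not tell which correlations were fixed in advance.

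**Working it through.** The documents state no figure for these analyses, so there is nothing to reproduce. The check is one of order, and then of what is left open.

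**Order of events**

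1. Primary clinical lock: clinical, safety and reactogenicity data to about 28 days after the last vaccination (Protocol 11.5.4).
2. From that lock, the SDCC may run unblinded analyses of safety and available immunogenicity data. Serology and processed systems biology data may be analysed as they arrive (Protocol 11.5.4). Protocol 4 counts cytokines and transcriptomes among the systems biology studies. The SDCC is also responsible for analysis and reporting (Protocol 15.1).
3. Primary CSR: all primary and secondary endpoints (SAP 6.2). By SAP 3.2 these include HAI, Neut, cytokines and the RNA-Seq differential expression counts.
4. Proteomics and correlation results: CSR addenda (SAP 6.2).
5. Deadline for the correlation plan: any time before the proteomics lock (SAP 12). No date ties that lock to steps 2 or 3.

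The plan therefore permits the RNA-Seq correlation addendum to be written after every one of its inputs has been analysed and reported by arm.

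**What is already fixed and what is open**

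| Element | Where fixed | Status |
|---|---|---|
| Predictor: baseline fold change in LCPM | Protocol 11.5.1.1 | Named |
| Cytokine concentrations, peak titer, seroconversion | Protocol 11.5.1.1; SAP 3.2, exploratory endpoints 5 and 6 | Named |
| Seroconversion definition | SAP 3.3 | Named |
| The 24 cytokines/chemokines | SAP Listing 9 | Named |
| Study days for titers and cytokines | SAP 3.2, exploratory endpoints 5 and 6 | Named |
| Model families (regularized canonical correlation; penalised linear and logistic regression) | Protocol 11.5.1.1 | Named |
| Tuning, use of Neut beside HAI, combining cell types and arms | Not stated | Open, secondary |
| Safety outcome | Not defined | Open |

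The main open choice is therefore the safety outcome.

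**Illustration of what an open choice can do**

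SAP 4.5.3 lists 6 local and 8 systemic solicited events, 14 in all. Suppose one fixed score with no true association is compared with each event at a two-sided 5% level.

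- Independent events: 1 − (1 − 0.05)^14 = 1 − 0.4877 = 0.512.
- Equicorrelated normal statistics, P(max |z| > 1.96) over 14: 0.35 at correlation 0.5 and 0.20 at correlation 0.8.

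The correlations, the single score and the 5% rule are all assumptions. The plan states none of them, so 20% to 51% shows a direction and rough scale only.

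**The case against.** Three arguments against the point have force.

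- **Most outcomes are already named.** A reader might infer that titer and cytokine outcomes can also be chosen late. The table above shows otherwise. This argument stands, and it limits the point to the safety outcome and some modelling detail.
- **Safety profiles cannot all be named in advance.** Exploratory Objective 7 in Protocol 3 is "Exploratory inspection of transcriptomics\proteomics response signatures for subjects with unexpected or severe safety profiles that are related to the study products", and what is unexpected cannot be listed beforehand. A reader might also infer that the protocol allows inspection and nothing more. It does not say that: Protocol 11.5.6 plans exploratory analysis of safety data alongside the transcriptomic and proteomic changes, and Protocol 4 plans integration with reactogenicity. Some guidance from the safety tables is therefore legitimate. What remains is that correlations found this way should not be called predictive, and that reactogenicity, which is solicited and graded on fixed scales, can be named in advance.
- **The stakes are low and the analyses are labelled.** Protocol 11.2 calls the study exploratory and hypothesis-generating, and these results go to CSR addenda. That stands, and it sets the weight of the point. It does not remove it, because such a study's product is its signatures.

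The addenda were not supplied. SAP 1 says the correlation analyses are presented in a separate addendum, and SAP 6.5 cites an Addendum A for proteomics imputation. If a dated addendum precedes the unblinded analyses, the timing concern is answered.

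**Conclusion.** The point holds in a limited form. SAP 12 sets a deadline that gives the RNA-Seq correlations no protection, and SAP 10 plans to draw the safety outcome from summaries that may by then be unblinded, in the same 30 subjects. No primary or secondary conclusion is affected.

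The documents do not support these stronger readings:

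- **That late selection happened.** The documents permit the sequence but do not show it. The unblinded analyses are optional, and the addenda and their dates are not to hand.
- **That the SAP plainly breaches the protocol.** Protocol 11.5 requires a detailed plan before database lock, but Protocol 11.5.4 itself sends the correlation analyses to CSR addenda and does not say which lock governs them.
- **That the plan has a 20% to 51% error rate.** The named methods are penalised regression and canonical correlation, with no p-value rule stated for them, and nothing says the 14 events will be tested one by one.

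The conclusion rests on the proteomics lock being free to fall after the primary analyses, which the reporting order in SAP 6.2 allows.

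**What to change.** - **SAP 12:** require the addendum for correlations between RNA-Seq and antibody, cytokine and safety data to be final before any unblinded analysis of those data. Let only the proteomics correlations wait for the proteomics lock.
- **SAP 10:** name one safety outcome in advance from the existing tables, for example the maximum severity of any systemic solicited event after each dose (Tables 135 and 136). Describe other safety correlations as descriptive inspection, and drop the word predictive for them.
- **If the data are already unblinded:** cite the date of any addendum finalised beforehand. If there is none, label the safety correlations post hoc in the CSR addendum.

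The cost is SAP wording and an earlier date for one addendum, with no change to data collection or participants. The downside is less freedom to choose outcomes later, though further correlations can still be reported as post hoc.

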13. REPORTING CONVENTIONS

P-values ≥ 0.0001 and ≤ 0.9999 will be reported to 4 decimal places; p-values less than 0.0001 will be reported as “<0.0001”; p-values greater than 0.9999 will be reported as “> 0.9999”. The mean, standard deviation, and any other statistics other than quantiles, will be reported to one decimal place greater than the original data. Quantiles, such as median, Q1, Q3, minimum and maximum will use the same number of decimal places as the original data.

15. LISTING OF TABLES, FIGURES, AND LISTINGS

Table, figure, and listing shells are presented in Appendices 1, 2, and 3.

APPENDICES

9.1 Overall Study Design and Plan Description**Table 1: Study Design and Sample Size**

Subjects	First Study Vaccination (Day 1)	Second Study Vaccination (Day 29±2 days)	Study Arm Label
10	15 µg A/H3N2v*	N/A	Study Arm 1 A/H3N2v, D1
10	3.75 µg A/H7N9 + AS03	3.75 µg A/H7N9 + AS03	Study Arm 2 A/H7N9 + AS03 D1, 29
10	3.75 µg A/H7N9+PBS	3.75 µg A/H7N9 + PBS	Study Arm 3 A/H7N9 + PBS, D1, 29
Total N=30 vaccinated subjects			

*Unadjuvanted

10.2 Protocol Deviations

Table 2: Distribution of Protocol Deviations by Category, Type, and Treatment Group

Category	Deviation Type	Study Arm 1 A/H3N2v, D1 (N=X)		Study Arm 2 A/H7N9 + AS03, D1, 29 (N=X)		Study Arm 3 A/H7N9 + PBS, D1, 29 (N=X)		All Subjects (N=X)	
		No. of Subj.	No. of Dev.	No. of Subj.	No. of Dev.	No. of Subj.	No. of Dev.	No. of Subj.	No. of Dev.
Eligibility/enrollment	Any type								
	Did not meet inclusion criterion	x	x			x	x	x	x
	Met exclusion criterion								
	ICF not signed prior to study procedures								
Treatment administration schedule	Other								
	Any type								
	Out of window visit								
	Missed visit/visit not conducted								
	Missed treatment administration								
Follow-up visit schedule	Delayed treatment administration								
	Other								
	Any type								
	Out of window visit								
	Missed visit/visit not conducted								
Protocol procedure/assessment	Other								
	Any type								
	Incorrect version of ICF signed								
	Blood not collected								
	Urine not collected								
	Other specimen not collected								
	Too few aliquots obtained								
	Specimen result not obtained								
	Required procedure not conducted								
	Required procedure done incorrectly								
Study product temperature excursion									

Table 2: Distribution of Protocol Deviations by Category, Type, and Treatment Group *(continued)*

Category	Deviation Type	Study Arm 1 A/H3N2v, D1 (N=X)		Study Arm 2 A/H7N9 + AS03, D1, 29 (N=X)		Study Arm 3 A/H7N9 + PBS, D1, 29 (N=X)		All Subjects (N=X)	
		No. of Subj.	No. of Dev.	No. of Subj.	No. of Dev.	No. of Subj.	No. of Dev.	No. of Subj.	No. of Dev.
	Specimen temperature excursion								
	Other								
Treatment administration	Any type								
	Required procedure done incorrectly								
	Study product temperature excursion								
	Other								
Blinding policy/procedure	Any type								
	Treatment unblinded								
	Other								
N=Number of enrolled subjects.									

12.2.2 Displays of Adverse Events**Solicited Adverse Event Grading Scale****Table 3: Local (Injection Site) Reactogenicity Grading**

Local (Injection Site) Reaction	Mild (Grade 1)	Moderate (Grade 2)	Severe (Grade 3)
Pain – experienced without touching the injection site (spontaneous discomfort)	Subject is aware of pain, but it does not interfere with daily activity, and no pain medication is taken	There is interference with daily activity or it requires repeated use of a non-narcotic pain reliever for >24 hours	Pain prevents daily activity or requires any use of a narcotic pain reliever
Tenderness – hurts only when injection site is touched or the arm is moved	The area immediately surrounding the injection site hurts only when touched or with arm motion, and it does not interfere with daily activity	The area immediately surrounding the injection site hurts when touched or with arm motion, and it interferes with daily activity	The area immediately surrounding the injection site hurts when touched or with arm motion, and it prevents daily activity
Pruritus (Itching)	Does not interfere with daily activity	Interferes with daily activity	Prevents daily activity
Ecchymosis (Bruising)*	Does not interfere with daily activity	Interferes with daily activity	Prevents daily activity
Erythema (Redness)*	Does not interfere with daily activity	Interferes with daily activity	Prevents daily activity
Induration (Hardness)/Swelling*	Does not interfere with daily activity	Interferes with daily activity	Prevents daily activity

* Will also be measured in mm but size will not be used as halting criteria.

Table 4: Local (Injection Site) Reactogenicity Measurements

Local (Injection Site) Reaction	Small	Medium	Large
Ecchymosis (Bruising)*	<20 mm	20 mm – 50 mm	>50 mm
Erythema (Redness)*	<20 mm	20 mm – 50 mm	>50 mm
Induration (Hardness)/Swelling*	<20 mm	20 mm – 50 mm	>50 mm

* Will not be used as halting criteria.

Table 5: Subjective Systemic Reactogenicity Grading

Systemic (Subjective)	Mild (Grade 1)	Moderate (Grade 2)	Severe (Grade 3)
Feverishness (Chills/Shivering/Sweating)	No interference with daily activity	Some interference with daily activity	Significant interference, prevents daily activity
Fatigue (Tiredness)	No interference with daily activity	Some interference with daily activity	Significant interference, prevents daily activity
Malaise (General Unwell Feeling)	No interference with daily activity	Some interference with daily activity	Significant interference, prevents daily activity
Myalgia (Body Aches/Muscular Pain)*	No interference with daily activity	Some interference with daily activity	Significant interference, prevents daily activity

Systemic (Subjective)	Mild (Grade 1)	Moderate (Grade 2)	Severe (Grade 3)
Arthralgia (Joint Pain)*	No interference with daily activity	Some interference with daily activity	Significant interference, prevents daily activity
Headache	No interference with daily activity	Some interference with daily activity	Significant interference, prevents daily activity
Nausea	No interference with daily activity	Some interference with daily activity	Significant interference, prevents daily activity

* Not at injection site.

Table 6: Quantitative Systemic Reactogenicity Grading

Systemic (Quantitative)	Mild (Grade 1)	Moderate (Grade 2)	Severe (Grade 3)
Fever* - oral†	38.0°C – 38.4°C 100.4°F – 101.1°F	38.5°C – 38.9°C 101.2°F – 102.0°F	>38.9°C >102.0°F

Note: Oral temperature assessed on Day 1 prior to the first study vaccination will be considered as baseline.

* A fever can be considered not related to the study product if an alternative etiology can be documented.

† Subjects must not eat or drink anything hot or cold, or smoke within 10 minutes prior to taking oral temperature.

Table 7: Additional Adverse Event Severity Grading

Physiologic Parameter	Mild (Grade 1)	Moderate (Grade 2)	Severe (Grade 3)
Bradycardia - beats per minute	45 – 49	40 – 44	<40
Tachycardia - beats per minute	116 – 130	131 – 155	>155
Hypotension (systolic) mm Hg	80 – 84	75 – 79	<75
Hypotension (diastolic) mm Hg	50 – 54	45 – 49	<45
Hypertension (systolic) mm Hg	151 – 155	156 – 160	>160
Hypertension (diastolic) mm Hg	96 – 100	101 – 105	>105

14.1 Description of Study Subjects**14.1.1 Disposition of Subjects****Table 8: Subject Disposition by Treatment Group – All Enrolled Subjects**

Subject Disposition	Study Arm 1 A/H3N2v, D1 (N=X)		Study Arm 2 A/H7N9 + AS03, D1, 29 (N=X)		Study Arm 3 A/H7N9 + PBS, D1, 29 (N=X)	
	n	%	n	%	n	%
Screened	x	--	x	--	x	--
Enrolled/Randomized	x	100	x	100	x	100
Received One Treatment	x	xx	x	xx	x	xx
Received All Scheduled Treatments ^a	x	xx	x	xx	x	xx
Completed Day 2 Omics Blood Draw	x	xx	x	xx	x	xx
Completed Day 4 Omics Blood Draw	x	xx	x	xx	x	xx
Completed Day 8 Omics Blood Draw	x	xx	n/a	n/a	n/a	n/a
Completed Day 29 Omics Blood Draw	n/a	n/a	x	xx	x	xx
Completed Day 30 Omics Blood Draw	n/a	n/a	x	xx	x	xx
Completed Day 32 Omics Blood Draw	n/a	n/a	x	xx	x	xx
Completed Day 36 Omics Blood Draw	n/a	n/a	x	xx	x	xx
Completed Follow-up (Study Day 29) ^a			n/a	n/a	n/a	n/a
Completed Follow-up (Study Day 366) ^a	n/a	n/a	x	xx	x	xx
Completed Per Protocol ^b	x	xx	x	xx	x	xx

N=number of enrolled subjects
^a Refer to Listing of Early Terminations or Discontinued Subjects for reasons subjects discontinued or terminated early.
^b Refer to Listing of Analysis Populations Exclusions for reasons subjects are excluded from the Analysis populations.

Table 9: Analysis Populations by Treatment Group and Time Point – All Enrolled Subjects

Analysis Populations	Time Point	Reason Subjects Excluded	Study Arm 1 (A/H3N2v, D1) (N=X)		Study Arm 1 (A/H3N2v, D1) (N=X)		Group 3 3.75 µg A/H7N9 + PBS (D1, 29) (N=X)	
			n	%	n	%	%	n
Safety Analysis Population	Any Time Point	Any Reason	x	xx	x	xx	x	xx
		[Reason 1, for example: Did not meet eligibility criteria]						
		[Reason 2]						
		[Reason 3]						
		[Reason 4]						
ITT Analysis Population	Any Time Point	Any Reason						
		[Reason 1]						
		[Reason 2]						
PP Analysis Population	Any Time Point	Any Reason						
		[Reason 1]						
		[Reason 2]						
	Day 29 (Post-Vaccination 1)	Any Reason						
		[Reason 1, for example: Did not meet eligibility criteria]						
		[Reason 2]						
		[Reason 3]						

N=Number of enrolled subjects.

Table 10: Ineligibility Summary of Screen Failures

Inclusion/Exclusion Category	Inclusion/Exclusion Criterion	n ^a	% ^b
Inclusion and Exclusion	Number of subjects failing any eligibility criterion	x	xx
Inclusion	Any inclusion criterion	x	xx
	[inclusion criterion 1]	x	xx
	[inclusion criterion 2]	x	xx
	[inclusion criterion 3]	x	xx
Exclusion	Any exclusion criterion	x	xx
	[exclusion criterion 1]	x	xx
	[exclusion criterion 2]	x	xx
	[exclusion criterion 3]	x	xx
Eligible but not enrolled		x	xx

^a More than one criterion may be marked per subject.

^b Denominator for percentages is the total number of screen failures.

